### **Statistical analysis**

We will use mixed linear modeling to assess for changes in butyrate and glucose metabolism before and after the tributyrin supplementation.

As a *post hoc* and only exploratory analyses we will regress differences in with tributyrin-induced changes of the various clinical and laboratory outcome measures.

Sample size estimation: This experiment is a first in human study of this drug for treatment of glucose changes in a neurodegenerative condition. There is a preliminary experiment of this safe drug conducted in high-fat fed mice that we base our same size justification off that showed mice receiving tributyrin showed a reduction in glucose levels compared to a comparator arm of approximately 13% with a standard deviation of 9% (PMID 22621868). If estimate a similar effect size in our cohort, estimating a mean plasma glucose of 110mg/dl at baseline, using a power of 0.8 and a two-sided alpha of 0.05 for our primary analysis that will compare pre and post tributyrin, we arrive at a total sample size of 20.

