# **Overall strategy**

#### Overview

The overarching goal of this small exploratory open-label pilot study is to explore [C]butyrate PET and [F]FDG PET glucose metabolism and clinical measures before and after open-label treatment with the SCFA prodrug tributyrin in a small pilot study in PD (n=8) and normal control older adults (n=2). Positive findings in this small exploratory pilot trial may support target engagement study of SCFA supplementation in normal adults and PD. PET and/or MRI Imaging protocols will be optional for a separate subset of 10 participants may also complete the study based on clinical or laboratory test battery alone for the exploratory hypothesis.

Timetable: This study, to be conducted over a 2-year period, will include a net total of n=20 subjects (NC, n=4; PD, n=16; total net; n=20; gross n=32 to allow for attrition). Details of the enrollment and major test procedures are listed in **table 1** below.

*Milestone* of recruitment success are net completion of 9 persons for year 1.

Table 1: Study enrollment & main       assessments	NC	PD	TOTAL
Baseline [  C]butyrate PET and [  F]FDG PET-CT & brain MRI with baseline clinical assessment	NC=2	PD=8	n=10
Post-intervention [  C]butyrate PET and [  F]FDG PET-CT & MRI	NC=2	PD=8	n=10
30-day (± 7) tributyrin intervention with pre/post clinical assessments)	NC=4	PD=16	n=20
Exploratory clinical and laboratory test battery pre and post the tributyrin supplement intervention	NC=4	PD=16	N=20
Total subject net recruitment aims 1 & 2	NC=4	PD=16	n=20*

Design: Exploratory open-label tributyrin supplementation pilot study.

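### The stated inputs do not give a sample size of 20 for a pre/post comparison; they give 5 to 10

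*Combined protocol and SAP*

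**What the plan says.** The Statistical analysis section bases the sample size on a preliminary mouse experiment that showed "a reduction in glucose levels compared to a comparator arm of approximately 13% with a standard deviation of 9" per cent. It adds a baseline by "estimating a mean plasma glucose of 110mg/dl at baseline", sets the error rates by "using a power of 0.8 and a two-sided alpha of 0.05 for our primary analysis", and says that this analysis "will compare pre and post tributyrin, we arrive at a total sample size of 20". It does not name the test, say whether 9% is an SD of change or an SD at one time point, or give a within-person correlation.

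The analysis itself is described in one sentence: "We will use mixed linear modeling to assess for changes in butyrate and glucose metabolism before and after" supplementation. No model terms are listed.

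The Overview describes an open-label study in which all participants receive tributyrin (4 controls and 16 people with PD), with "total net; n=20; gross n=32 to allow for attrition". Average glucose from the continuous monitor is one of the two primary outcomes (Outcome measures).

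**The concern.** The paragraph is written as a derivation, with inputs followed by a result, so it can be checked. A 13% effect with a 9% SD is 1.44 SDs. A within-person test needs very few people for an effect that large, and 20 looked too many by a factor of two or more.

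What is at stake is the justification, not the safety of the number. A reader is told that 20 people are what 80% power for a 13% fall requires. If that does not follow, the power of a primary endpoint rests on an unstated calculation. The SD used also comes from a comparison between arms in mice, whereas a pre/post calculation needs the SD of within-person change. This is the only sample size justification in the document.

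**Working it through.** **Inputs** (Statistical analysis, unless noted)
- Fall of 13%, SD 9%: standardised effect 13/9 = 1.444.
- Baseline 110 mg/dl: 13% is 14.3 mg/dl and 9% is 9.9 mg/dl. The ratio is still 1.444, so the baseline does not affect the result.
- Power 0.80, two-sided alpha 0.05.
- 20 completers, net of attrition (Overview).
- *Assumption:* the mixed model has time plus a random intercept. With two time points and complete pairs, its test of time is the paired t-test.
- *Assumption:* pre/post correlation ρ between 0 and 0.75, since the plan gives none.

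**Formula.** With d = 13 / SD of change, power comes from the noncentral t distribution with n − 1 degrees of freedom and noncentrality d√n. The required n is the smallest with power of at least 0.80.

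**Attempt to reproduce 20: 9% as the SD of change.** n = 5 gives 68.0% and n = 6 gives 80.5%, so the answer is 6.

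**Attempt to reproduce 20: 9% as the SD at each time point.** With equal SDs, SD of change = 9 × √(2(1 − ρ)).

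| ρ | SD of change | n for 80% | Power at that n |
|---|---|---|---|
| 0.75 | 6.4% | 5 | 91.9% |
| 0.5 | 9.0% | 6 | 80.5% |
| 0.25 | 11.0% | 8 | 81.5% |
| 0 | 12.7% | 10 | 81.9% |
| −0.5 | 15.6% | 14 | 82.2% |
| −1 (limit) | 18.0% | 18 | 82.3% |

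No correlation gives 20.

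**Other routes tried, with SD of change 9%.** One-sided 5% gives 5. Two-sided alpha 0.025, for two primary outcomes, gives 8 (6 to 12 over ρ from 0.75 to 0). Power of 90% gives 8. Mixing scales (13 over 9.9) gives 7.

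**Two independent groups, d = 1.444.** 8 per arm gives 76.6%, 9 per arm (18 in total) gives 82.0%, and 10 per arm (20 in total) gives 86.3%. This is the closest match, but 20 is still not the smallest total that reaches 80%.

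**Power of 20 completers for a 13% fall.** Above 99.9% if the SD of change is 9%, 99.1% if 12.7%, 95.7% if 15%, and 78.7% if 20%. The 15% and 20% are illustrative and have no source in the documents.

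**What 20 pairs can detect.** Power of 80% at n = 20 requires d = 0.660. For 20 to be the answer for a 13% fall, the SD of change would have to be 13 / 0.660 = 19.7%, or 14.3 / 0.660 = 21.7 mg/dl, more than twice the stated 9%.

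**The case against.** The strongest reply is that nothing shown is miscalculated; the calculation is under-described. The plan names no test and does not define the SD, and the paired model is supplied here. The effect comes from a comparison between arms, and a two-group calculation gives 18, close to 20. So the likely fault is a between-group calculation described as pre/post. The 110 mg/dl baseline does no work if both inputs are percentages, which could mean that an SD in mg/dl was used and not printed. Ten people measured twice, at correlation 0, would also make 20 measurements. Finally, this is a small exploratory pilot, the error is on the safe side and enrolment would not change.

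Part of this stands. The origin of the 20 cannot be known, and a two-group calculation is a plausible source. The consequence is limited to the justification. The rest does not rescue the figure. A two-group calculation does not fit a study with no comparator arm. The Overview counts 20 subjects, not measurements. An unprinted SD is conjecture, and if one was used, the printed inputs are not those behind the number. A pilot need not claim 80% power, but this one does, for a named primary comparison.

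**Conclusion.** The concern holds. The printed inputs do not give 20 for a pre/post test. They give 6 if 9% is the SD of change, and 5 to 10 if 9% is the SD at each time point with correlation 0.75 to 0. The exact figure depends on the assumed model and correlation, but the conclusion does not: with equal SDs, the most extreme correlation possible needs 18. Dropout is already handled by the gross figure of 32.

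The error is conservative. On the plan's own assumptions the glucose endpoint is not underpowered, and with correlation 0 or higher 20 completers have about 99% power or more. What is missing is a basis for the human SD of change. If it were 20%, power for a 13% fall would be 78.7%, and the plan gives no means of judging which value applies. It should be corrected, but it does not threaten the conduct of the study.

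**What to change.** Keep 20 completers. Delete the statement that 20 follows from 13% and 9% at 80% power, and replace it with text such as:

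> Twenty completers give 80% power (paired, two-sided 5%) to detect a change of 0.66 SD of the within-person change in mean sensor glucose. The SD of change is not known. As assumptions for illustration, the detectable change is 5.9% (6.5 mg/dl) if that SD is 9%, 8.4% (9.2 mg/dl) if 12.7%, 9.9% (10.9 mg/dl) if 15%, and 13.2% (14.5 mg/dl) if 20%. The pilot will estimate this SD and report it with the 95% confidence interval for the change.

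The detectable changes are 0.660 times each SD, converted at the 110 mg/dl baseline. If the sponsor did use another test or another SD to reach 20, the paragraph should state it and explain how it fits a single-arm pre/post design. The cost is wording only, with no change to enrolment.

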# Pitfalls, problems and alternative strategies

Ineligibility and attrition rate:

### Protection of Human Subjects

#### i) Human Subjects

Description of subject populations:

- i) Healthy control persons, M/F, age 45 years and over without a history of neurological or psychiatric disease or significant GI disease or uncontrolled medical comorbidity will be recruited (net n=4).
- ii) PD (net n=16) Diagnosis of PD in PD participants (M/F, age 45 years and over) will based on the United Kingdom Parkinson's Disease Society Brain Bank Diagnostic Research Criteria (patients with clinically significant dementia will be excluded (i.e., fails informed assent screening criteria and has significant evidence of iADL functions, such as ability to take own medications while administering the pre-consent screening questionnaire).

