#### Table 3: Neuropsychological characterization

able 5. Neuropsychological characterization				
Overall mental status	Montreal Cognitive Assessment Scale 			
	PD-Cognitive Rating Scale 			
Intelligence	WAIS-IV: Information 			
Attention & Cognitive	n-back test (OPTIONAL)  , Stroop Color Word			
Control	Interference Test 9			
	WAIS-IV: Digit Span (5)			
	WAIS-III: Digit Symbol-Coding 			
Language	Boston Naming Test (30 item) 			
	Controlled Oral Word Association Test (Phonemic &			
	Semantic)			
Learning & Memory	California Verbal Learning Test – II 			
Visuospatial/Construction	Clock drawing 			
	Benton Judgment of Line Orientation 			
Executive/Working	D-KEFS: Color Word Test, Verbal Fluency Test, Trail			
Memory	Making Test, Sorting Test 			
	WAIS-IV Matrix Reasoning, Digit Backwards 			
Information processing	D-KEFS: Trail Making Test 			
speed	WAIS-III: Digit Symbol-Coding 5, 23			
	Reaction time			

capsule) will be used as 1 capsule tid with meals (total of 1.5 g of tributyrin per day). If the patient cannot tolerate tributyrin we will lower the dose to one bid and if this is not tolerated than to once per day (e.g. at evening) and if this is not tolerated we will withdraw the study participant from the study. The participant will be asked to complete a daily drug diary while taking tributyrin. All supplement bottles will be returned at the end of the study for a drug accountability check.

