### Exclusion criteria:

1. *Exclusion*: (a) subjects with contra-indications to MR imaging, including pacemakers or severe claustrophobia (for participants undergoing imaging); (b) Evidence of large vessel stroke or mass lesion on MRI; (c) Regular use of anti-cholinergic, benzodiazepines or neuroleptic drugs, (d) history of significant GI disease, (e) significant metabolic or uncontrolled medical cormorbidity, (f) poorly controlled diabetes, (g) pregnancy or breast feeding, (h) dementia requiring informed assent, (i) suicidal ideation.

Recruitment: Subjects will be recruited from the University of Michigan Movement Disorder clinics, UM research studies website, and/or advertisement/flyers.

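### Does the reversed iADL clause in the PD dementia exclusion leave the trial without a usable eligibility rule?

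*Combined protocol and SAP*

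**What the plan says.** Under Protection of Human Subjects, i) Human Subjects, item ii), the protocol describes the PD group (net n=16) and states that "patients with clinically significant dementia will be excluded". A bracket then explains what this means: the person "fails informed assent screening criteria and has significant evidence of iADL functions, such as ability to take own medications". The evidence is gathered "while administering the pre-consent screening questionnaire".

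The separate list headed Exclusion criteria contains, among nine items, "h) dementia requiring informed assent". That item mentions no everyday function and is not confined to PD.

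Neither place defines the assent screening criteria, sets a threshold for everyday function, or cross-refers to the other. Table 3 lists the "Montreal Cognitive Assessment Scale" and the PD-Cognitive Rating Scale as part of the test battery, with no eligibility cut-off attached.

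**The concern.** The bracket joins two conditions with a conjunction, and the second is illustrated by an ability rather than a loss. Taken at its word, someone who fails the assent screen and cannot manage medications does not meet the definition of excluded dementia, while someone who fails it and can manage them does. That is back to front, in the only sentence that spells the exclusion out.

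The clause also matters to the trial. It bears on capacity to consent. Staff may obtain a waiver of consent during the screening call for fasting and withholding dopaminergic medication, for people not yet consented (Methods). The supplement is taken at home with a daily diary.

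Putting the missing word back might not end the matter. The PD description would then require screen failure and functional loss together, while item (h) has no functional test. Screening staff could be left with two rules that do not quite match.

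**Working it through.** No figure in the plan is in dispute, so the check sets the two rules side by side. Each person is classed by three facts: fails the assent screen or not, everyday function intact or impaired, dementia present or not. That gives 2 × 2 × 2 = 8 combinations.

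Rules compared:
- **L**: PD description as written (fails and function intact).
- **R**: PD description with the missing word restored (fails and function impaired).
- **H1**: item (h) read as dementia plus screen failure.
- **H2**: item (h) read as screen failure alone.
- **H3**: item (h) read as shorthand for the restored PD description.

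H1 to H3 assume that requiring assent is the same as failing the assent screen. The four combinations in which the screen is passed are excluded by none of the five. The other four are:

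| Case (screen failed) | L | R | H1 | H2 | H3 |
|---|---|---|---|---|---|
| 1. Function intact, dementia | out | – | out | out | – |
| 2. Function intact, no dementia | out | – | – | out | – |
| 3. Function impaired, dementia | – | out | out | out | out |
| 4. Function impaired, no dementia | – | out | – | out | out |

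*The person the literal wording misses.* Among people with dementia this is case 3. Item (h) excludes case 3 on all three readings, so the slip in the PD description does not let that person in.

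*Both passages applied together.* A person is out if either passage excludes them.
- With H2: L or H2 gives cases 1–4; R or H2 gives cases 1–4. Restoring the word changes nobody.
- With H1: L or H1 gives 1, 2, 3; R or H1 gives 1, 3, 4. Among people with dementia both give 1 and 3, so again nobody changes. Cases 2 and 4 concern people without dementia, who are outside the stated target of the exclusion.
- With H3: L or H3 gives 1–4; R or H3 gives 3 and 4. Here the literal wording can only exclude too many (cases 1 and 2). It admits nobody extra.

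*Does a mismatch survive the correction?* Compare R with each reading of (h). Against H3 there is none. Against H1 they differ in case 1 and, for people without dementia, case 4. Against H2 they differ in cases 1 and 2. For people with dementia the only possible residual difference is therefore case 1, and it depends on how item (h) is read.

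*Effect on the statistics.* The sample size of 20 is derived "using a power of 0.8 and a two-sided alpha of 0.05 for our primary analysis" from an assumed glucose change and its standard deviation. No eligibility term enters that calculation or the mixed model.

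**The case for a change.** The strongest reply is that intent settles only the direction of the clause. It does not tell staff whether failing the assent screen is enough alone. On the plain wording of item (h) no functional test applies, the documents nowhere say that its word dementia borrows the PD description, and the phrase about failing the assent criteria is itself open: it could mean needing assent or being unable to give it. With 16 PD completers planned, each eligibility decision counts, and one sentence would cure it.

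Part of this stands. The clause is wrong as written, and the reading under which the two passages agree is natural but not stated. A reading that carried the literal, reversed clause into item (h) as well would leave case 3 uncovered, but it would require taking the same obvious slip at face value twice, against the word dementia in both places.

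The rest carries less weight. That staff work from two conflicting rules is not shown: the check is made with a pre-consent questionnaire that is not in the documents. The lack of a cut-off on the cognitive scales is no contradiction either, because the protocol chose an exclusion based on capacity and function, and a score threshold would be a different design preference.

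**Conclusion.** The concern is right about the wording but does not call for a change to the plan. A word is missing; the governing statement that clinically significant dementia is excluded fixes the meaning; and the same sentence shows other slips of the pen (a missing verb before the diagnostic criteria, a bracket opened and not closed). Any screener would read it as intended.

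In size: of the four screen-failure combinations, the one that the reversal would wrongly let through (dementia with lost function) is excluded by item (h) on all three readings tested. After correction, one combination among people with dementia (screen failed, function kept) may be treated differently by the two passages, and only if item (h) is not shorthand for the PD description. Which rule was meant for that person is for the sponsor to say. The documents give no counts of screened people in any combination, so the expectation of few if any wrong enrolments rests on the cumulative use of exclusions, not on data.

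The conclusion assumes that requiring assent means failing the assent screen and that both passages are applied. On that footing a correction would tidy the text without altering the sample size, the visits, the analysis or what the trial can conclude.

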### Exclusion criteria:

1. *Exclusion*: (a) subjects with contra-indications to MR imaging, including pacemakers or severe claustrophobia (for participants undergoing imaging); (b) Evidence of large vessel stroke or mass lesion on MRI; (c) Regular use of anti-cholinergic, benzodiazepines or neuroleptic drugs, (d) history of significant GI disease, (e) significant metabolic or uncontrolled medical cormorbidity, (f) poorly controlled diabetes, (g) pregnancy or breast feeding, (h) dementia requiring informed assent, (i) suicidal ideation.

Recruitment: Subjects will be recruited from the University of Michigan Movement Disorder clinics, UM research studies website, and/or advertisement/flyers.

### ii) Sources of Materials:

Information gathered specifically for this research project includes test results from clinical test scales, psychometric cognitive measures, neurobehavioral rating scales, clinical motor data, questionnaires, and data derived from the butyrate and FDG PET and from brain MRI.

#### iii) Potential Risks:

Confidentiality of Research Information: The research data to be collected from subjects will consist of confidential information relating to clinical, motor, cognitive, neurobehavioral and neuro-imaging functions. These research data are not intended for entry into the subjects' clinical medical records. However, the data remain potentially discoverable. This may lead to violation of privacy and embarrassment of the subject.

Clinical Testing: Risks in regard to the clinical assessment are limited to fatigue, frustration, discomfort, and momentary embarrassment that may occur when one experiences difficulty performing a task or learning a new skill.

Risks associated with clinical, neuropsychological and behavioral testing: This study involves cognitive tests and questionnaires. The cognitive tests are not harmful but some people find them frustrating and concerning. Risks in regard to the neuropsychological and behavioral assessment are limited to fatigue, frustration and momentary embarrassment that may occur when one experiences difficulty performing a task or learning a new skill. Some people may be uncomfortable/embarrassed disclosing personal information or become a little nervous about memory testing, and may experience discomfort or become tired. Study team members are very well experienced in the assessment of older individuals and persons with dementia, understanding the need for breaks, gentle reassurance, or reinforcement. All assessments will be stopped if requested by the participant.

MRI scan: There is a substantial risk to persons who have metallic objects inside their bodies, as the magnet in the MR scanner can cause these to move. Consequently, participants with pacemakers or metallic objects located in the eye, ear, brain or blood vessel walls will be excluded. Participants who developed claustrophobic anxiety during scanning found that this fear dissipated within 15 min while remaining in the scanner, or as necessary, after exiting the scanner. There also is the potential that imaging could reveal a previously unrecognized but pre-existing abnormality. Many such abnormalities are not clinically significant, but they may cause anxiety or require further investigation by a personal physician. If one of the investigators identifies such an abnormality, they will contact the personal physician, who will arrange for appropriate care.

PET-CT scans & venipuncture: Insertion of a catheter for intravenous injection of the PET radiopharmaceutical may be commonly associated with slight pain or bruising at the puncture site and rare chance of infection. Participation in this research study will involve low level exposure to radiation associated with the PET, CT and DEXA scans.

Certified staff will be in attendance at all times during the study. A physician will be available and an emergency cart is located in the PET Facility for treatment of any adverse reactions that may occur.

During the course of this study, the participant will be exposed to radiation from the two [C]butyrate PET, the two [F]FDG PET-CT and two DEXA scans. The risks associated with the amount of radiation exposure participants receive in this study are considered very rare and comparable to every day radiation exposure risks.

The biological effect of radiation in humans is measured in terms of Sieverts (Sv) or mSv (1/1000 Sv), which is a unit of uniform whole body exposure. The maximum radiation exposure (assuming a person will complete all 4 PET scans) a participant will receive from the CT, [C]butyrate PET and [F]FDG PET scans is equivalent to a uniform whole body dose of 21.2 mSv, which is approximately 42.4% of the annual radiation exposure (50 mSv) permitted to radiation workers by federal regulations. The participant will be instructed to use the bathroom and urinate as soon as possible

after the PET scans to minimize bladder exposure. The radiation the participant will be exposed to from each DXA scan is 0.0310 mSv, which is significantly less than 1% of the permitted annual radiation exposure.

There is no known minimum level of radiation exposure that is recognized as being totally free of the risk of causing genetic defects (cellular abnormalities) or cancer. However, the risk associated with the amount of radiation exposure that you will receive from this study is considered to be low. The risk of a side effect from this level of radiation exposure is very rare. The risk from radiation exposure of this amount is considered to be similar to other everyday risks, such as driving a car.

No PET studies will be performed on pregnant, nursing, or potentially pregnant women.

A urine pregnancy test will be performed on all women of childbearing potential within 48 hours prior to the PET scanning session, and urine sampling may be performed on subjects at baseline and post-interventions as an additional screening measure.

Risks associated with tributryin: The risks to participants are very minimal. Although tributyrin is taken for symptoms of irritable or inflammatory bowel disease it is possible that nausea or indigestion may occur. However, these gastrointestinal side effects are both rare and mild. Tributyrin is received GRAS (Generally Regarded As Safe) certification from the FDA, is commercially available in the United States and prior work has shown that the dosing regimen proposed in this study has been found to be safe and generally well-tolerated.

**Data Study Monitoring Plan (DSMP):** Drs. [name] and [name] will act as the Data Safety Monitoring Plan members for this study. All adverse events and other study related events will be discussed at monthly investigator meetings. Study team will document any adverse events specifically related to study participation (imaging, clinical visit, at-home supplement and/or device usage, etc.). Adverse events will be classified according to standard criteria and reported to the IRBMED (relevant University of Michigan IRB) according to standard guidelines. Serious adverse events will be reported within 24 hours.

For risk of suicidality (if participants select answer responses 2 or 3 for question 9 on the Beck Depression Inventor, i.e. 'I would like to kill myself' (answer 2) or 'I would like to kill myself if I had a chance' (answer 3) then the staff will hand out the UM Depression brochure, refer to the contact information and also inform [name] or [name] who will discuss this with the participant. The face to face conversation with the physicians must occur during that visit and must not be deferred. There must be a safety plan in place before the patient can leave the building.

